5.1 Contraception requirements

Please refer to exclusion criteria ([Section 4](#)) for details of contraception requirements for the study.

5.2 Prohibited treatment

Use of the treatments displayed in the table below is NOT allowed after the start of study drug until the end of study evaluation.

Table 5-1 Prohibited treatment

Medication	Action to be taken
Iodine (radioactive or cold)	Withdrawal may be required on a case-by-case basis
Methimazole	
Propylthiouracil	
Amiodarone	
Live vaccinations	Withdrawal immediately

Patients may continue the medications that had been taken before enrolling in this study and may take medications that are permitted per protocol. Doses may be titrated if deemed necessary by their physicians.

5.3 Dietary, fluid, smoking, and other restrictions

Patients should maintain their usual diet and life habits during the entire study.

6 Treatment

6.1 Study treatment

Details on the storage and management of study medication and instructions for prescribing and taking study treatment are outlined in Section 3 of the Site Operations Manual (SOM).

6.1.1 Investigational treatment

The investigational drug, CFZ533 will be available as lyophilisate in dose strength of 150 mg. CFZ533 will be packed and labeled under responsibility of drug supply management department of Novartis and will be supplied to the Investigator sites as open label bulk supply.

6.2 Treatment arms

Patients will receive CFZ533 intravenously at 10 mg/kg over approximately one hour on Study Day 1, Day 15, Day 29, Day 57, and Day 85.

6.3 Permitted dose adjustments and interruptions of study treatment

Study drug dose adjustments and/or interruptions are not permitted UNLESS safety finding(s) warrant it at the discretion of the investigator (See [Section 7.4](#)).

6.4 Treatment assignment

All patients who are eligible to participate in the study will be assigned to study treatment (see Site Operations Manual for more details). The investigator will enter the treatment number on the CRF.

6.5 Treatment blinding

This is a non-confirmatory, open-label, one treatment arm study.

Corporate Confidential Information

6.6 Emergency breaking of assigned treatment code

Not applicable.

6.7 Treatment exposure and compliance

The IV infusion will be given at the study site, therefore, compliance is ensured. In addition, pharmacokinetic exposure will be measured in all patients treated with CFZ533, as detailed in [Section 8.5](#).

6.8 Recommended treatment of adverse events

Parenteral administration of monoclonal antibodies can be associated with acute, severe reactions (occurring within the first few hours post dose) secondary to hypersensitivity, immunogenicity, or ADCC-mediated cell depletion.

Injection site reactions can also be noted during or after subcutaneous administration and are usually less severe than infusion reactions, however, may still require medical attention and treatment.

In this study, CFZ533 will be administered as an intravenous infusion.

Corporate Confidential Information

In the

event of a hypersensitivity reaction, **stop the infusion**. Assess and treat for anaphylaxis, if indicated, and initiate supportive care per local practice. Fluids, vasopressors, corticosteroids, antihistamines, bronchodilators, and oxygen should be on hand.

Patients will be monitored at the site for at least 2 hours or longer after the completion of IV infusion at the discretion of the Investigator to ensure adequate safety monitoring. In case of any signs of an acute reaction, clinical treatment will be provided as determined by the treating physician on a case-by-case basis and depending on the severity. For the management of allergic reaction, anaphylaxis and cytokine release, it is recommended to follow the guidelines by the National Cancer Institute Common Toxicity Criteria ([CTCAE 2010](#)).

Medication used to treat AEs must be recorded on the Concomitant medications/Significant non-drug therapies CRF.

6.9 Rescue medication

Patients may receive standard of care treatment for Graves' hyperthyroidism at the discretion of the investigator in case of worsening of the disease. Patients will be discontinued from the study in this case as described in [Section 7.1](#). Rescue medication is to be provided by the study center or personal physician.

Use of rescue medication must be recorded on the Concomitant medications/Significant non-drug therapies CRF after start of study drug.

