2.2 Secondary objective

Objective	Endpoint

To assess the safety and tolerability of CFZ533 (10 mg/kg IV for 12 weeks) up to 36 weeks	
Adverse events

[figure not shown]
Corporate Confidential Information

3 **Investigational plan**

3.1 **Study design**

This is a non-confirmatory, open-label, one treatment arm study in patients with GD.

A total of approximately 15 patients will be enrolled and treated with CFZ533 to ensure approximately 12 completers. For each patient, the study will consist of a screening epoch of up to 28 days, a baseline evaluation, a 12-week treatment epoch, 24-week follow up epoch after the last dosing of CFZ533 on Study Day 85, and a study completion evaluation on Study Day 253. Patients who discontinue the drug before having completed 4 weeks of treatment and 4 week efficacy and safety evaluations will be replaced with a newly enrolled patient. The study completion assessments (End of Study; EOS) should be completed in patients who discontinue the study. The study design is presented in [Figure 3-1](#).

Figure 3-1 Study design

Patients who meet the eligibility criteria at screening will be admitted to baseline evaluations. Baseline evaluations may be started from Day -7 to allow completion of assessments prior to the treatment on Study Day 1. All baseline safety evaluation results must be available prior to dosing and meeting the eligibility criteria. The baseline visit (Visit 99) can be skipped and the baseline assessments would be completed prior to the study treatment on Day 1 (Visit 101) if Day 1 is scheduled within 7 days of the screening visit (Visit 1).

Eligible patients will enter the study to receive treatment with CFZ533 at 10 mg/kg IV over approximately one hour on Study Day 1. Patients will be monitored closely for at least 2 hours, at the discretion of the Investigator, after the completion of IV administration of CFZ533 for vital signs and adverse events, including development of an injection reaction.

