Eligible patients will visit the study center in the morning of Study Days 1, 15, 29, 57 and 85 for IV administration of CFZ533. PK/PD blood samples will be collected as defined in the assessment schedule in [Table 8-1](#) and safety assessment will be conducted for 2 hour or longer after completion of each IV infusion, at the discretion of the Investigator. Following satisfactory review of safety data by the Investigator, patients will be discharged from the site on the same day after completion of all assessments, provided there are no safety concerns.

Patients will return to the site periodically for the follow up assessment (safety, PK and PD) on Study Days 113, 141, 169, 211, and 253 as defined in the [Assessment table](#). Days for follow-up visits may be slightly flexible based on the patients' schedule. More information about visit windows can be found in the SOM.

The end of study visit/assessment will occur on Study Day 253, which will include study completion evaluations followed by discharge from the study.

Throughout the study, patients can remain on their standard of care therapies established prior to treatment with study drug, unless outlined otherwise in this protocol, provided that the treatments are maintained at a constant level during the study.

Safety, PK and PD assessment will be taken at various time points as defined in [Table 8-1](#). Safety assessments will include physical examinations, ECGs, vital signs, standard clinical laboratory evaluations (hematology, blood chemistry, urinalysis, pregnancy test, blood coagulation), and adverse event and serious adverse event monitoring. Immunogenicity assessments will be performed before, during and after the treatment period.

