Corporate Confidential Information

Therefore, 12-week of treatment with CFZ533 is considered to be necessary and sufficient to test the hypothesis whether or not CFZ533 could be a potential treatment for GD. In addition, follow up duration may be extended up to 365 days (52 weeks) if clinically relevant efficacy was observed during the treatment period or up to 5-month of full CD40 RO. The clinical relevant efficacy is referring to normalization of TSH after 12 week treatment with CFZ533. Another important endpoints are effects of CFZ533 on free T4 and total T3 after 12 weeks of treatment. Extended follow up of a patient will be terminated when a standard of care rescue therapy is initiated for treating Graves' hyperthyroidism.

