7.1 Discontinuation of study treatment

Patients may voluntarily discontinue study treatment for any reason at any time.

The investigator **must** discontinue study treatment for a given patient if, on balance, he/she believes that continuation would be detrimental to the patient's well-being.

Study treatment **must** be discontinued under the following circumstances:

- Patient withdraws consent
- Pregnancy
- Grade 3 or higher allergic reaction
- Acute, Grade 3 or higher infection as judged by the Investigator

The study treatment should be discontinued if:

- Clinically significant worsening of Graves' disease, eg. beta-blocker unable to control the symptoms of hyperthyroidism, at the discretion of the Investigator.
- New onset atrial fibrillation or angina.
- On balance, the investigator believes that continuation would be detrimental to the patient's well-being.

Discontinuation of study treatment will be at the discretion of the Investigator, under the following circumstances:

- Use of prohibited treatment as per [Section 5.2](#).
- Any other protocol deviation that results in a significant risk to the patient's safety

Patients who discontinue study treatment or who decide they do not wish to participate in the study further should NOT be considered withdrawn from the study UNLESS they withdraw their consent (see [Section 7.3](#)). Where possible, they should return for the assessments defined in the [Assessment table](#). If they fail to return for these assessments for unknown reasons, every effort (e.g. telephone, e-mail, letter) should be made to contact them as specified in [Section 7.2.1](#). Patients who discontinue the drug before having completed 4 weeks of treatment and 4 week efficacy and safety evaluations will be replaced with a newly enrolled patient.

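### Protocol 6.9 takes rescued patients off the study while 7.1, which it cites, keeps them in follow-up, and the SAP does not secure how they count in the TSH responder proportion

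*Protocol*

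**What the plan says.** **Follow-up after rescue.** Protocol 6.9 lets the investigator give standard-of-care treatment if the disease worsens, and adds: "Patients will be discontinued from the study in this case as described in" Section 7.1. Section 7.1 is about stopping study treatment. Patients who stop "should NOT be considered withdrawn from the study UNLESS they withdraw their consent", and "Where possible, they should return for the assessments defined in the" assessment table. Worsening of Graves' disease appears there as a reason to stop study treatment. So does use of prohibited treatment, which includes anti-thyroid drugs and iodine, but under a softer lead-in: "Discontinuation of study treatment will be at the discretion of the Investigator, under the following circumstances". Table 5-1 makes withdrawal for these agents a case-by-case matter.

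Protocol 3.3 ends only the optional extension at rescue: "Extended follow up of a patient will be terminated when a standard of care rescue therapy is initiated". Protocol 3.1 schedules the "follow up assessment (safety, PK and PD) on Study Days 113, 141, 169, 211, and 253" and provides that "The study completion assessments (End of Study; EOS) should be completed in patients who discontinue the study". The secondary objective in 2.2 is "To assess the safety and tolerability of CFZ533 (10 mg/kg IV for 12 weeks) up to 36 weeks".

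**Analysis.** SAP section 4 names two rescue categories, oral corticosteroids and anti-thyroid drugs, and says their use is not a protocol deviation. Post-rescue values are flagged in listings and drawn in red on individual profiles, but left out of summaries and inferential analyses. The missing-at-random justification is given for the longitudinal models. Protocol 11.4.3 and SAP 6.1.3.1 treat patients who discontinue after the week-4 assessment as TSH non-responders, unless the last recorded TSH came after 8 weeks and exceeded 0.35 mU/L. Neither mentions rescue, and neither says whether discontinuing refers to the drug or the study.

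**The concern.** Two instructions for the same patient point in different directions. A site that follows the words of 6.9 would end scheduled visits at rescue. A site that follows 7.1 would continue them. The follow-up at stake carries the 36-week safety objective in about 15 patients.

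The same ambiguity reaches the primary TSH test. A patient rescued after week 4 who stays in follow-up, as 7.1 asks, may have a week-12 TSH that SAP section 4 excludes. If that patient does not count as having discontinued, no sentence gives a responder status. The analyst could then count a non-responder, carry a pre-rescue value forward, or leave the patient out. Leaving out patients whose disease worsened enough to need rescue raises the response rate. The missing-at-random argument does not help here, because the primary test is an exact test on a proportion and not a longitudinal model.

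There is also a coding gap. Protocol 3.2 counts radio-iodine as standard of care, and Table 5-1 prohibits it. It is in neither SAP rescue category, so rescue with it could be caught by the Table 4-1 row on prohibited medication that interferes with efficacy, which removes the subject from the PD analysis.

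**Working it through.** **1. Follow-up at stake under a literal reading of 6.9** (days from Protocol 3.1)
- Rescued by Day 85: 253 − 85 = 168 days = 24 weeks, with five visits (Days 113, 141, 169, 211, 253).
- Rescued just after Day 169: 253 − 169 = 84 days = 12 weeks, with two visits (Days 211, 253).
- In both cases 3.1 asks for end-of-study assessments at discontinuation, so not everything is lost.

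**2. The plan's own TSH figures** (Protocol 11.4.2 and 11.6; SAP 6.1.3). Inputs: n = 12, null rate 5%, assumed rate 38%, one-sided exact test at 10%, success at 3 or more responders.
- P(X ≥ 3 | 12, 0.05) = 0.0196 and P(X ≥ 2 | 12, 0.05) = 0.1184, so 3 is the correct cut-off.
- P(X ≥ 3 | 12, 0.38) = 0.893, against a stated power of around 89%.
- The lower limit of the exact 80% interval for 3/12 is 0.0957, against a stated value of about 10%.

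The plan's figures reproduce.

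**3. Effect of the denominator with 2 responders.** The p-value is P(X ≥ 2 | n, 0.05) = 1 − 0.95^n − n × 0.05 × 0.95^(n−1). For n = 12 this is 1 − 0.5404 − 0.3413 = 0.118. For n = 10 it is 1 − 0.5987 − 0.3151 = 0.086.

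| Denominator | p for 2 responders | Criterion (p ≤ 0.10) |
|---|---|---|
| 15 | 0.171 | not met |
| 13 | 0.135 | not met |
| 12 | 0.118 | not met |
| 11 | 0.102 | not met |
| 10 | 0.086 | met |

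Three responders are needed for n = 11 to 15 and two for n = 6 to 10 (the range checked). Starting from 12 patients, dropping one changes nothing and dropping two lowers the requirement from 3 to 2. Starting from 15, five would have to be dropped. The number rescued is an assumption throughout.

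**4. Does the text decide the denominator?**
- If discontinuing means leaving the study, 6.9 makes the rescued patient a non-responder, but 7.1 keeps that patient in the study and outside the rule.
- If it means stopping the drug, the worsening item in 7.1 normally brings the patient under the rule. However, 7.1 leaves stopping for prohibited treatment to the investigator, so rescue does not strictly imply stopping.
- Usage elsewhere is mixed. Protocol 3.1 and 7.1 and SAP 1.4 word the week-4 replacement rule in terms of the drug, while Protocol section 4 words it in terms of the study.

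**The case against.** The strongest reply is that the documents already answer most of this. Section 6.9 defers to 7.1, which is emphatic, and 7.2 requires every enrolled patient to complete the whole study. The SAP's post-rescue listings and profiles show that the analysis team expected visits to continue. On the analysis side, the SAP excludes values, not subjects. It also says that rescue with corticosteroids or anti-thyroid drugs is not a deviation, so such a patient stays in the PD set. The non-responder rule applies whatever the reason for discontinuing, and a patient rescued for worsening will usually have stopped the drug.

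Much of this stands. It makes non-responder the most natural reading. It does not remove the contradiction between 6.9 and 7.1, and it does not settle the responder status of a patient who is rescued, stays in follow-up and has an excluded week-12 value.

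A reader might infer that the SAP instructs rescued patients to be dropped; no sentence does. A reader might also infer that the type I error exceeds 10%. That result can be obtained by fixing two certain non-responders among 12 and raising the rate in the other ten to 0.05 × 12/10 = 0.06, which gives P(X ≥ 2 | 10, 0.06) = 0.118. It depends on that constructed null. If the 5% null applies to the ten analysed, the figure is 0.086, below 10%.

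**Conclusion.** The contradiction between 6.9 and 7.1 is clear on the page and should be removed. Its largest cost is 168 days and five visits for a patient rescued by Day 85, apart from end-of-study assessments. That is the cost if a site applies 6.9 literally, and nothing in the documents shows that any site would.

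The analysis point is narrower. The natural reading keeps a patient rescued after week 4 in the denominator as a non-responder, but the wording does not guarantee it, and the alternative favours the drug. The conclusion would change only with exactly 2 responders and a denominator of 10 or fewer, which means at least two rescued patients dropped from 12 or five from 15. The documents give no rescue rate, so how likely this is cannot be judged. In a small, non-confirmatory, single-arm study meant to inform further development, this calls for a clarification and does not undermine the test.

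**What to change.** - **Protocol:** reconcile 6.9 with 7.1 so that all sites apply one rule on scheduled follow-up after rescue. Which rule applies is for the sponsor and investigators to decide.
- **SAP 6.1.3.1, before database lock:** add that a patient rescued after the week-4 assessment stays in the TSH responder denominator and is handled under the existing rule using pre-rescue values only. That patient is a non-responder unless the last pre-rescue TSH was taken after 8 weeks of treatment and was above 0.35 mU/L.
- **SAP section 4:** extend the rescue coding to radio-iodine, so that rescue with it does not remove the patient from the PD set through the prohibited-medication row of Table 4-1.

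The cost is amendment wording in Protocol 6.9, one sentence in SAP 6.1.3.1 and one coding change in SAP section 4. The analysis changes need no new visits or data.

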6.10 Concomitant treatment

Patients may be treated with any medications that are not listed as prohibited treatment, as standard of care for their medical conditions by their physicians. Use of beta-blockers for treating the symptoms of Graves' disease during participation in this study is permitted at the discretion of the treating physician. Medication, amount and frequency of use must be recorded.

The investigator should instruct the patient to notify the study site about any new medications he/she takes after the start of the study drug.

Administration of acetaminophen is acceptable at the discretion of treatment physicians, but must be documented.

Should a patient have an incidental and limited need for a medication to be taken within the restricted pre-dose timeframe (e.g. acetaminophen for a headache, antibiotic prophylaxis prior to dental surgery, etc.), the sponsor should be advised, as administration of any concomitant medication may require the patient to be replaced. Decisions regarding replacements will be discussed with the sponsor on a case-by-case basis.

All prescription medications, over-the-counter drugs and significant non-drug therapies (including physical therapy and blood transfusions) administered or taken within the timeframe defined in the entry criteria prior to the start of the study and during the study, must be recorded on the Concomitant medications/ Significant non-drug therapies section of the CRF.

Medication entries should be specific to trade name, the amount of single doses and units, the dosing frequency, route of administration, the start and discontinuation dates, and the medical reason for the therapy.

7 Discontinuation and study completion

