In patients receiving weekly to bi-monthly administration of the parent antibody lucatumumab, the rate of infection was very low and similar to control, supporting these stated hypotheses. Patients with current, active or latent infection susceptible to reactivation will be excluded from entry into the present clinical study.

The risk of infection may increase if CFZ533 is combined with steroids or strong immunosuppressive drugs. Patients who are HIV-positive or have taken immunomodulatory drugs, such as cyclosporine A, methotrexate, and/or cyclophosphamide within 3 months at the baseline will be excluded.

Patients enrolled in the current study will be monitored regularly and carefully for signs and symptoms which might indicate a severe infection. Patients will be informed to contact the study physician if they present with signs and symptoms of an infection such as fever, nausea, myalgia, headache, arthralgia, chills, diarrhea, stiff neck, and malaise for further assessment and treatment if necessary.

Lymphadenopathy

Corporate Confidential Information

The investigator should pay special attention to lymph nodes in patients during physical assessments including unusual lymphadenopathy in the absence of infection.

Lymphoproliferative disorders

Corporate Confidential Information

The clinician should monitor hematology regularly for changes consistent with a lymphoproliferative disorder.

Pregnancy

Women of child bearing potential should be informed that taking the study drug may involve unknown risks to the fetus if pregnancy were to occur during the study and agree that in order to participate in the study they must adhere to the contraception requirement for the duration of the study. If there is any question that the subject will not reliably comply, they should not be entered in the study.

Thrombosis

It has been shown that monoclonal antibodies that bind to CD154 (CD40L), the natural ligand to CD40, are associated with a risk of thrombosis in both clinical studies and non-clinical studies in primates. Accordingly, the potential risk of thromboembolic events with CFZ533 has been thoroughly investigated during the process of development.

Corporate Confidential Information

Although the risk is hypothetical, hematologic and coagulation parameters will be regularly monitored in the current study.

Systemic inflammation and potential kidney injury

Corporate Confidential Information

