4.2 Exclusion criteria

Patients fulfilling **any** of the following criteria are NOT eligible for inclusion in this study. No additional exclusions may be applied by the investigator, in order to ensure that the study population will be representative of all eligible patients.

1. Use of other investigational drugs within 5 half-lives prior to first treatment.
2. History of hypersensitivity to vaccines, the study drug or to drugs of similar chemical classes (e.g. IgG₁-related biologic agents).
3. History of treatment of Graves' disease with radio-iodine ablation or thyroidectomy.
4. Current treatment with anti-thyroid drugs (methimazole or propylthiouracil) within one week of starting treatment. Discontinuation of ATD must not have been for the sole purpose of qualifying for this study; rather it should have been based on clinical considerations (e.g. lack of efficacy or safety/tolerability issues with ATD).
5. History of hyperthyroidism not caused by Graves' disease (e.g. toxic multinodular goiter, autonomous thyroid nodule, or acute inflammatory thyroiditis).
6. History or presence of thyroid storm (fever, profuse sweating, vomiting, diarrhea, delirium, severe weakness, seizures, markedly irregular heartbeat, yellow skin and eyes (jaundice), severe low blood pressure, and coma).
7. Previous treatment with a B cell-depleting biologic agent or any other immunomodulatory biologic agent (experimental or approved) within 5 half-lives prior to first treatment.
8. History of malignancy of any organ system (other than localized basal cell carcinoma of the skin), treated or untreated, within the past 5 years, regardless of whether there is evidence of local recurrence or metastases.
9. Significant illness which has not resolved within two weeks prior to initial dosing.
10. History of recurrent clinically significant infection or of recurrent bacterial infections with encapsulated organisms, including current, active or latent infection susceptible to reactivation.
11. History of primary or secondary immunodeficiency, including a positive HIV (ELISA and Western blot) test result at screening.
12. A positive Hepatitis B surface antigen or Hepatitis C test result at screening.
13. History or evidence of tuberculosis by either of the following tests at screening:
 - Positive PPD skin test (size of induration measured after 48-72 hours, and a positive result is defined as an induration of $\geq 5\text{mm}$ or according to local practice/guidelines) **OR**

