Corporate Confidential
Information

- Positive QuantiFERON TB-Gold test

14. A negative Epstein Barr virus (EBV) test (as defined in the laboratory manual) at screening.

15. Any of the following abnormal laboratory values at screening (may be repeated one time for a single outlying value):

- Total white blood count (WBC) outside of the range $2.0-15.0 \times 10^9/L$
- Absolute neutrophil count $<1.5 \times 10^9/L$
- Lymphocyte count $<0.8 \times 10^9/L$
- Platelets $< 100 \times 10^9/L$
- Hemoglobin $< 9.0 \text{ g/dl}$

16. Severe liver disease or liver injury as indicated by abnormal liver function tests at screening:

- Any **single parameter** of ALT, AST, γ -GT, must not exceed $>5 \times$ the upper limit of normal (ULN);
- alkaline phosphatase (ALP) must not exceed $>5 \times$ the upper limit of normal (ULN);
- serum total bilirubin (TBL) must not exceed $>1.8 \times$ the upper limit of normal (ULN) except if the elevation is due to Gilbert's syndrome.

If necessary, laboratory testing may be repeated on one occasion (as soon as possible) prior to randomization, to rule out any laboratory error.

17. Inability or unwillingness to undergo repeated venipuncture (e.g., because of poor tolerability or lack of access to veins).

18. Donation or loss of 400mL or more of blood within eight (8) weeks prior to initial dosing or longer, if required by local regulation.

19. Plans for immunization with a live vaccine within a 2-month period before enrollment or during the study period.

20. History or evidence of drug or alcohol abuse within the 6 months prior to dosing, or evidence of such abuse as indicated by the laboratory assays conducted during screening.

21. Treatment with immunomodulatory drugs, such as cyclosporine A, methotrexate, and/or cyclophosphamide within 3 months from baseline. Glucocorticosteroid therapy with prednisolone up to 10 mg daily is permitted if patients are on stable dose for more than 3 months before enrollment in the study.

22. History or presence of coronary artery disease, ventricular or atrial arrhythmias (including atrial fibrillation) with the exception of sinus tachycardia controlled with beta-blockers.

23. Pregnant or breast-feeding women, where pregnancy is defined as the state of a female after conception and until the termination of gestation, confirmed by a positive hCG laboratory test.

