11.6 Sample size calculation

The proposed sample size for this study is 12 patients (to complete the study). Assuming CFZ533 is associated with 38% normalization of the TSH levels after 12 weeks of treatment (which is consistent with the response rate seen with Rituximab in 26 weeks in one small, open-label study ([Heemstra et al 2008](#)), there is around 89% power to detect a proportion of TSH responders significantly higher than 5% (this would be achieved with at least 3/12 responders), with a type I error of 10%. Additionally, this sample size provides 98% power to detect normalization of the total T3 (and free T4, respectively) below the upper limit of the normal range (2.79 nmol/L and 22.7 pmol/L, respectively). The assumed baseline levels are 7.2 nmol/L for total T3 and 58.55 pmol/L for free T4, which are the average values reported in GD patients in [Andrade et al \(2001\)](#). The assumed standard deviation for the change from baseline are 4.24 nmol/L and 34.58 pmol/L respectively.

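### Immunomodulatory drugs barred at entry are missing from the on-study prohibited list, and the SAP has no rule for hormone values after a newly started non-steroid one

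*Protocol*

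**What the plan says.** **At entry.** Protocol 4.2, exclusion 21, bars "Treatment with immunomodulatory drugs, such as cyclosporine A, methotrexate, and/or cyclophosphamide within 3 months from baseline", with an allowance for stable low-dose prednisolone. Exclusion 7 bars "Previous treatment with a B cell-depleting biologic agent or any other immunomodulatory biologic agent" when last used within five half-lives of the first dose.

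**Stated risk.** Protocol 3.6.2, under infections, says: "The risk of infection may increase if CFZ533 is combined with steroids or strong immunosuppressive drugs". The next sentence gives the entry exclusion as the safeguard. The opening paragraph of 3.6.2 also names avoiding prohibited treatments among the general measures that limit risk, and refers to the Investigator's Brochure for detail.

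**On study.** Protocol 5.2 says: "Use of the treatments displayed in the table below is NOT allowed after the start of study drug until the end of study evaluation". The items listed in Table 5-1 are iodine, methimazole, propylthiouracil, amiodarone and live vaccinations. The text below it adds that patients "may take medications that are permitted per protocol". Section 6.10 is broader: "Patients may be treated with any medications that are not listed as prohibited treatment, as standard of care for their medical conditions by their physicians".

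**In the analysis.** Protocol 11.4.1 and SAP 6.1.1 define a TSH responder by a value above 0.35 mU/L after 12 weeks, with no condition on other drugs. SAP Section 4 removes from the PD analysis patients who took prohibited drugs that interfere with efficacy. It also drops datapoints after rescue medication, which has two codes: oral corticosteroids (O01) and anti-thyroid drugs (O02). SAP 6.1.3.1 counts patients who discontinue after the week-4 assessment as non-responders, unless their last TSH was after 8 weeks of treatment and above 0.35 mU/L.

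**The concern.** The entry rules treat these agents as unacceptable in a patient about to receive CFZ533, yet the on-study rules permit them from the first dose. The stated mitigation relies on a prohibited list that does not contain them.

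Two things are at stake. The trial has one arm and no control, so a hormone response that follows a newly added immunomodulator cannot be separated from a response to CFZ533, and no analysis rule sets those values aside. The secondary objective is safety, and infections under combined immunosuppression would be tabulated together with infections under CFZ533 alone.

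**Working it through.** **1. The rules side by side**

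| Agent class | Entry (Protocol 4.2) | Named in the 3.6.2 risk sentence | Table 5-1 | Later PD data (SAP Section 4) |
|---|---|---|---|---|
| Anti-thyroid drugs | barred within one week | no | listed | excluded, rescue code |
| Oral corticosteroids | stable prednisolone up to 10 mg daily allowed | yes | not listed | excluded, rescue code |
| Cyclosporine A, methotrexate, cyclophosphamide and similar | barred within 3 months | yes, as strong immunosuppressants | not listed | no rule |
| B-cell-depleting and other immunomodulatory biologics | barred within 5 half-lives | no | not listed | no rule |

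The analysis gap is in the last two rows. A permitted drug is not a prohibited drug, and starting one is not a deviation, so neither SAP route applies.

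**2. Clauses that might close the gap**

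- Protocol 3.1 (therapy kept constant) covers only therapy established before study drug.
- Protocol 6.9 discontinues patients given standard of care for worsening Graves' hyperthyroidism. Section 3.2 describes that care as anti-thyroid drugs, radio-iodine or surgery, so a drug started for another disease is not reached.
- The replacement sentence in 6.10 concerns incidental use in a restricted pre-dose period.
- Protocol 7.1 leaves stopping to investigator judgement, or to prohibited treatment or another protocol deviation. It governs study treatment and does not say which values are analysed.

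**3. The plan's own figures**

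Inputs from Protocol 11.4.2 and 11.6: n = 12, null 5%, one-sided exact test at 10%, success at 3 or more responders, assumed response 38%.

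- Power at 38%: 1 − (0.62^12 + 12 × 0.38 × 0.62^11 + 66 × 0.38² × 0.62^10) = 0.893. The stated figure of around 89% reproduces.
- The exact (Clopper-Pearson) 80% lower bound at 3/12 is 0.096, which matches the stated value of about 10%.

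**4. What one patient changes**

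- P(X ≥ 3) at 5% = 1 − (0.5404 + 0.3413 + 0.0988) = 0.020: success.
- P(X ≥ 2) at 5% = 1 − (0.5404 + 0.3413) = 0.118: failure at 10%.

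**5. Illustration under assumptions**

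Suppose CFZ533 has only the 5% null rate, and k of the 12 patients start such an agent and respond at rate q. The chance of 3 or more responders is the upper tail of Binomial(12 − k, 0.05) + Binomial(k, q). For k = 1 and q = 38%: 0.38 × 0.1019 + 0.62 × 0.0152 = 0.048.

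| | q = 20% | q = 38% | q = 60% |
|---|---|---|---|
| k = 0 | 0.020 | 0.020 | 0.020 |
| k = 1 | 0.033 | 0.048 | 0.067 |
| k = 2 | 0.051 | 0.103 | 0.188 |

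Both k and q are assumptions; the documents give neither. The 38% is the plan's planning value, described as one "which is consistent with the response rate seen with Rituximab in 26 weeks", so it is not a week-12 rate for a drug started during the study.

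**6. Cost of counting starters as non-responders**

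At a 38% response, with the rule still 3 or more of 12, power is the upper tail of Binomial(12 − k, 0.38): 0.893, 0.852, 0.798 and 0.729 for k = 0, 1, 2 and 3.

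**The case against.** The scenario is narrow. Section 6.10 allows drugs as standard of care for a patient's conditions, and treatment for worsening Graves' disease leads to discontinuation. What remains is a patient who was free of these agents at entry and starts one for another disease before the week-12 sample. No rate is given and it may be low. The study is non-confirmatory, concomitant drugs are recorded with dates and reasons and listed by patient, infections have their own table, and the SAP provides for an amendment to its deviation table before database lock. The entry exclusion is a real and consistent safeguard for the infection risk. The Investigator's Brochure and the withheld infection text may add more.

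Most of this stands, and it limits the weight of the point. It does not supply a rule: listing a drug does not say whether the TSH value after it counts. In an open-label trial that choice should not be made once results are visible.

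A reader might also infer more than the documents support:

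- *That the protocol names B-cell biologics as a hazard with CFZ533.* The risk sentence in 3.6.2 covers steroids and strong immunosuppressive drugs. Biologics appear only as an entry exclusion.
- *That a patient who starts oral steroids still counts on later values.* The SAP already treats oral corticosteroids as rescue and drops later data.
- *That the rituximab benchmark shows these agents would normalise TSH by week 12.* It is one drug, in one small open-label study, at 26 weeks. Nothing in the documents speaks to methotrexate, cyclosporine A or cyclophosphamide.
- *That the 3/12 against 2/12 contrast measures this problem.* It holds for any single misclassified patient under this rule.

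**Conclusion.** The point holds as an inconsistency between entry and on-study rules and as a missing analysis rule for newly started non-steroid immunosuppressants and immunomodulatory biologics. It does not show that the primary result will be biased, because the frequency of such starts and their effect on TSH by week 12 are both unknown.

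The consequence is bounded from one side only: the decision can turn on a single patient (p = 0.020 against 0.118). Under the assumed inputs above, one or two starters would raise the chance of false success from 0.020 to between 0.033 and 0.188. Because the correction is cheap and the SAP already applies the same principle to oral corticosteroids and anti-thyroid drugs, it should be made before database lock.

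**What to change.** **Protocol.** Reconcile 3.6.2, exclusions 7 and 21 in 4.2, Table 5-1 and 6.10, so that entry rules, on-study rules and the stated mitigation agree. Which agents to restrict during the study is a clinical decision for the sponsor.

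**SAP Section 4.** Whatever the sponsor decides, add newly started non-steroid immunosuppressants and immunomodulatory biologics (the agents of exclusions 7 and 21) to the categories whose later PD data are excluded. Exclusion 21 gives examples only, so attach a drug list.

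**SAP 6.1.3.1.** This rule is written for patients who discontinue, and a starter may stay on study. State that the patient remains in the responder denominator and that the existing rule applies to the values left: non-responder unless the last TSH before the start was after 8 weeks of treatment and above 0.35 mU/L. For total T3 and free T4, use the last value before the start under the existing 8-week condition. Automatic non-response for every starter would be stricter than the plan's own handling of rescue and discontinuation, and is not needed.

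**Cost.** Protocol wording, a short SAP addition and a drug list; concomitant medication is already collected and coded. A patient who needs such a drug for another disease may count as a non-responder, so the response rate and power may be slightly lower (0.893 to 0.852 for one of 12).
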